2 STUDY OBJECTIVE

2.1 Primary Objective

Aim 1: To evaluate whether BATA produces changes in neural responses to reward anticipation and reward outcomes using high field fMRI that exceed our a priori target engagement criteria (right caudate nucleus (CN) activation during reward anticipation and decrease rostral anterior cingulate cortex (rACC) activation during reward outcomes) and exceed changes due to MBCT, an active comparison treatment.

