4.8 Screen failure procedures

If more than 4 weeks elapse between the baseline screen and the first scan session, this will be considered a screen fail and the individual will not be randomized.

5 STUDY EVALUATIONS AND MEASUREMENTS (how measurements will be made)

1) fMRI data (primary endpoint) will be collected at the UNC Biomedical Research Imaging Center (BRIC) at week 0, week 8, week 12, and week 15. Analyses of fMRI target engagement will focus on activation in the right CN during reward anticipation, the rACC during reward outcomes, and bilateral amygdala in response to threat. Data will be preprocessed using FSL (Oxford University, UK). We will ensure groups do not differ in head motion by calculating mean framewise displacement which yields, for each participant, a value indicating mean head displacement from one volume to the next. Hypotheses will be evaluated with a ROI approach whereby signal intensities are extracted from ROIs for the relevant task contrasts (i.e., potential win versus non-win trials during MID reward anticipation trials; wins versus non-wins during MID reward outcome trials; fearful and angry faces > shapes during the threat task). ROI analyses will be followed-up with whole-brain analyses that will yield activation maps thresholded at a False Discovery Rate of 0.01 to allow for an examination of activation in other reward processing regions, including the ventral striatum/nucleus accumbens, putamen, ventral tegmental area, and orbitofrontal cortex. To optimize BOLD signal coverage in the ventral

tegmental area we will acquire high-resolution T1-weighted images with 1x1x1 mm voxel size to allow for precise registration and will use cardiac and respiratory gated imaging during the acquisition of structural scans to address pulsatile artifacts using retrospective corrections implemented with the FSL PNM toolbox.

2) The Snaith–Hamilton Pleasure Scale (SHAPS) is a measure of anhedonia used to verify inclusion criteria. It is a well-validated 14-item self-report questionnaire that is administered by computer.

3) DSM diagnoses will be made using the SCID5, a semi-structured patient interview, and will be used to verify inclusion criteria

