6 STATISTICAL CONSIDERATION

6.1 Primary Endpoint (fMRI)

Increase in right CN activation during reward anticipation and decrease in rACC activation during reward outcomes.

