6.4 Statistical Methods

Aim 1, fMRI outcomes: Only patients who complete at least two therapy sessions will participate in post-treatment assessments. We will compare fMRI activation in regions of interest at pre- and post-treatment. The design is a 2 (BATA vs MBCT) X 2 (CN, rACC) X 2 (pretreatment vs post-treatment) ANCOVA testing the change from pre- to post-treatment as moderated by treatment group and brain region in the outcome variables. The Treatment × Time interaction beta will be used to evaluate whether BATA produces changes in neural responses to reward anticipation and reward outcomes that exceed our *a priori* target engagement criteria (increased right caudate nucleus (CN) activation during reward anticipation and decreased rostral anterior

cingulate cortex (rACC) activation during reward outcomes) and exceed changes due to MBCT. *Post-hoc* comparisons will compare change across each region.

Aim 2, anhedonia outcomes: To evaluate the effects of BATA, relative to MBCT, for on anhedonia symptoms treating anhedonia, we will test for differential change over time between those who receive BATA and those who receive MBCT post-treatment. We will use an intent-to-treat (ITT) analysis for patients who receive BATA relative to those who don't. The ITT model will be a repeated-measures ANCOVA with effects for treatment condition (BATA, MBCT), outcome measure (SHAPS), time (pre-treatment, post-treatment) and their interactions. The interaction tests will assess mean differences at each time point as well as differences in the degree of change between the groups. This also provides tests of each group relative to their baseline scores. We will include gender and age as covariates in these models.

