6.5 Sample Size and Power

Power Analyses: In this study we will enroll 60 participants, whom will receive BATA treatment MBCT treatment. Based on our pilot data demonstrating increased right CN activation during reward anticipation and decreased rACC activation during reward outcomes, we calculated an effect size of approximately $z=4.1$. Conservatively, we estimate the effect size for the increased right CN activation and reduced rACC activation will be in the range of $z = (0.75-1.25)$. Our models thus have >90% power at $\alpha=0.025$.

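### The Aim 1 test named in Section 6.4, one Treatment × Time beta from a joint CN/rACC model, either averages two effects predicted to go in opposite directions or tests only one region

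*Combined protocol and SAP*

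**What the plan says.** Section 6.4 sets out the Aim 1 model: "The design is a 2 (BATA vs MBCT) X 2 (CN, rACC) X 2 (pretreatment vs post-treatment) ANCOVA". It describes the model as testing pre-to-post change moderated by arm and by brain region. It then names the deciding quantity: "The Treatment × Time interaction beta will be used to evaluate whether BATA produces changes in neural responses to reward anticipation and reward outcomes", judged against the target engagement criteria and against MBCT. For the separate regions it adds only that post-hoc "comparisons will compare change across each region". The Statistical and Analytic Plan in the synopsis repeats the design without naming a term.

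The primary endpoint in Section 6.1 has two parts with opposite signs: "Increase in right CN activation during reward anticipation and decrease in rACC activation during reward outcomes". Section 2.1 joins the same two criteria and adds the comparison with the other arm: "activation during reward anticipation and decrease rostral anterior cingulate cortex (rACC) activation during reward outcomes) and exceed changes due to MBCT".

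Section 5 says "Hypotheses will be evaluated with a ROI approach whereby signal intensities are extracted from ROIs for the relevant task contrasts", and the contrasts differ by region: "potential win versus non-win trials during MID reward anticipation trials; wins versus non-wins during MID reward outcome trials".

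Section 6.5 says "Conservatively, we estimate the effect size for the increased right CN activation and reduced rACC activation will be in the range of" *z* = 0.75–1.25, and claims more than 90% power at alpha 0.025.

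**The concern.** Once region is a factor in the model, a two-way Treatment × Time coefficient has two ordinary meanings, depending on how region is coded.

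- **Averaged over region** (sum coding, or no three-way term). It is the mean of the CN and rACC treatment effects. Effects of opposite sign offset, completely if they are equal in raw units and partly otherwise. The average also mixes anticipation signal with outcome signal.
- **Reference coding.** It is the treatment effect in the reference region. The other criterion is reached only by the post-hoc comparisons.

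The plan does not say which applies. It also gives no sign reversal for rACC, no separate models by region, and no decision based on the three-way term. Section 1.2 does not expect MBCT to raise striatal reward activation, so the between-arm effects can be expected to keep their opposite signs.

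The primary result could therefore depend on a software default. The averaged version can miss the predicted pattern, and it can be significant for a pattern that contradicts it.

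**Working it through.** **Inputs.** From the documents: 60 randomized 1:1, so 30 per arm; effect size 0.75–1.25 in each region; alpha 0.025; >90% power. Assumed, because the documents do not say: *z* is a between-arm standardized difference in change; no dropout; alpha is two-sided unless stated; the CN–rACC correlation of change, r, lies between -0.3 and 0.5; SD ratios as shown.

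**1. The plan's own >90%, at 0.75 and alpha 0.025.**
- Between arms, one region: noncentrality 0.75 × √(30/2) = 2.905 on 58 df. Power is 72.6% two-sided, 81.5% one-sided.
- Within BATA only, n = 30: noncentrality 0.75 × √30 = 4.108 on 29 df. Power is 95.4% two-sided.
- Between arms, one region, two-sided, at larger effects: 93.9% at 1.0 and 99.4% at 1.25.

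So >90% can be reached on a within-arm reading, or between arms toward the upper part of the range. Because *z* and the sidedness are undefined, this does not prove the figure wrong. The within-arm test is not the beta named in Section 6.4.

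**2. What the named beta estimates.** Write δ for BATA change minus MBCT change in a region, in raw units.

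| δ(CN) / δ(rACC) | averaged: (δ(CN) + δ(rACC))/2 | CN reference | rACC reference |
|---|---|---|---|
| +0.75 / -0.75 | 0 | +0.75 | -0.75 |
| +1.25 / -0.75 | +0.25 | +1.25 | -0.75 |

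Fitting the 2×2×2 model to noise-free cell means gives these values.

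**3. Power of the averaged beta.** With d1, d2 in each region's own SD (s1 for CN, s2 for rACC):

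d = (d1·s1 + d2·s2) / √(s1² + s2² + 2·r·s1·s2), noncentrality = d·√15, 58 df, two-sided 0.025.

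For example, with equal SDs and r = 0, +1.25/-0.75 gives d = 0.50/√2 = 0.354, noncentrality 1.369 and power 18.4%. If both regions rise 0.75, d = 1.50/√2 = 1.061, noncentrality 4.108 and power 96.2%.

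Ranges over r from -0.3 to 0.5:

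| SD ratio CN:rACC | +0.75/-0.75 | +1.25/-0.75 | +0.75/+0.75 (against prediction) |
|---|---|---|---|
| 1:1 | 2.5% | 13–26% | 85–99% |
| 2:1 | 12–22% | 60–88% | 84–98% |
| 1:2 | 12–22% | 3–4% | 84–98% |

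At 3:1 with +1.25/-0.75, power is 82–96%. The beta then mainly reflects CN and does not show that rACC fell.

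**4. Is the three-way term enough?** Here d = (d1·s1 - d2·s2) / √(s1² + s2² - 2·r·s1·s2). At +0.75/-0.75 with equal SDs, power is 90% or more over the same range of r. But when only CN moves by 0.75 it is still significant 32–73% of the time (52–85% at 2:1, CN larger). It shows that the regions differ, not that each moved as predicted.

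**5. Region-specific rules at ±0.75, simulated, 30 per arm.**
- Both regions, each at two-sided 0.05: 64–69% (about 94% at ±1.0, over 99% at ±1.25).
- Either region, each at two-sided 0.025: 89–97%.
- Both regions, each at two-sided 0.025: 48–56%.
- Both at two-sided 0.05 when only CN moves by 0.75: 1.0–2.4%. When both regions rise by 0.75: below 0.01%.

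**The case against.** The best defence is that the plan means a separate Treatment × Time beta for each region. One averaged beta cannot be judged against two directional criteria, so the sentence makes sense only region by region. Section 6.4 mentions moderation by region, Section 5 describes region-of-interest extraction with a contrast for each, and alpha 0.025 looks like 0.05 split over two tests. The regional comparisons are planned in any case and would show the pattern.

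That reading is plausible, and if it is the intention the fix is one sentence. But it needs words the plan does not contain. Section 6.4 makes region a factor in a single model, names one two-way term, and labels the regional comparisons post hoc, with no alpha, direction or success rule. Nothing ties the 0.025 to two regional tests.

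Three parts of the objection stand. The power figures depend on assumed SD ratios and correlations; across those assumptions, power for effects in the predicted direction runs from 2.5% to 96%, so they illustrate the problem and do not measure it. Total cancellation needs equal and opposite raw effects, which no section predicts. Reading the word joining the two criteria as a both-regions rule is an interpretation, so the team must state its own choice.

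**Conclusion.** The concern holds, and it should be settled before the analysis. As written, the quantity named for the primary aim is either a regional average in which the predicted effects offset or a test of one region. The plan has no confirmatory test of CN up together with rACC down. That conclusion follows from the model and the named term and needs no numerical assumption.

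The size does need assumptions: the between-arm reading of *z*, 30 per arm without dropout, two-sided 0.025, and the assumed correlations and SDs. With equal SDs the averaged beta has 2.5% power at +0.75/-0.75, yet is significant in 85–99% of trials in which both regions rise by 0.75. The >90% in Section 6.5 is not shown to be wrong, but the plan does not show that it applies to the named term.

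**What to change.** In Section 6.4, and in the synopsis to match:

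1. Name two primary contrasts: Treatment × Time in right CN during anticipation (BATA greater than MBCT) and in rACC during outcomes (BATA less than MBCT).
2. State the success rule. The synopsis objective and Sections 2.1, 6.1 and 6.4 join the criteria with a conjunction, so the rule closest to the text is that both must succeed in the predicted direction, each at two-sided 0.05 with no split. If success in either region is intended, test each at two-sided 0.025 and limit the claim to the region that passes.
3. Keep Treatment × Region × Time as supportive.
4. Report BATA's own pre-to-post change in each region with a confidence interval before claiming target engagement.

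In Section 6.5, define *z* as within-arm or between-arm, state the sidedness of alpha, and give power for the chosen rule.

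This costs wording and a recalculated power figure, with no new data. The figure may be less favourable. On the between-arm reading at ±0.75 with 30 per arm, the both-regions rule has 64–69% power and the either-region rule 89–97%. With an assumed 24 per arm these become 47–55% and 80–92%. Reaching 90% for both regions at ±0.75 would take about 46–48 per arm, so the team should choose the rule knowing this. If *z* is within-arm, the >90% can stand for that test, but it does not cover the comparison with MBCT.

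### Aim 1 asks that BATA's own change meet the target engagement criteria and also exceed MBCT's, but section 6.4 assigns both questions to a between-arm interaction that can answer only the second

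*Combined protocol and SAP*

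**What the plan says.** Section 2.1 asks whether BATA's changes "exceed our a priori target engagement criteria", which it describes by region: the right caudate while reward is anticipated, and a fall in rACC when reward is received. It then adds a second condition: "and exceed changes due to MBCT, an active comparison treatment". Section 6.1 gives the primary endpoint as a direction with no comparator: "Increase in right CN activation during reward anticipation and decrease in rACC activation during reward outcomes".

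Section 6.4 describes a treatment by region by time model, an "ANCOVA testing the change from pre- to post-treatment as moderated by treatment group and brain region in the outcome variables". It assigns both conditions to one quantity: the Treatment × Time "interaction beta will be used to evaluate whether BATA produces changes in neural responses to reward anticipation and reward outcomes". The remaining Aim 1 analysis is described as post hoc: "comparisons will compare change across each region". No test of BATA's change against its own baseline is named for Aim 1. For Aim 2, the same section says of the SHAPS model: "This also provides tests of each group relative to their baseline scores".

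Section 6.5 states more than 90% power at α = 0.025 for effects of 0.75 to 1.25. It does not say whether these are within-arm or between-arm effects, or whether α is one- or two-sided.

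**The concern.** The interaction coefficient tells us how far the arms differ in change. It does not tell us whether BATA's caudate response rose or its rACC response fell. The first half of Aim 1 is a statement about BATA's own movement, and the quantity assigned to it cannot show that movement.

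At stake is what the primary result means. A favourable interaction could come from a BATA improvement, or from a worsening under MBCT while BATA stayed flat, or from a fall in both arms with BATA falling less. Only the first matches the stated criterion. If the result is reported as BATA target engagement on the strength of the interaction, the plan as written gives a reader no pre-specified way to tell these cases apart.

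**Working it through.** **Inputs.** 60 randomised 1:1, so n = 30 per arm (synopsis). α = 0.025 (section 6.5), taken as two-sided. Assumptions: SD of change = 1, no dropout, and the MBCT shifts below, for which the documents give no figure.

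**The plan's power figure.** With effect d in units of the SD of change:
- Between-arm interaction: noncentrality d√(n/2), 58 df. At d = 0.75 this is 0.75 × √15 = 2.90, and power is 72.6% (81.5% if α is one-sided). It is 93.9% at d = 1.0 and 99.4% at d = 1.25.
- Within-BATA change: noncentrality d√n, 29 df. At d = 0.75 this is 0.75 × √30 = 4.11, and power is 95.4%.

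The stated figure holds across the whole range only on the within-arm reading. The documents do not say which reading was used, so it cannot be called reproduced. It does show that the two questions have different power and need separate statements.

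**What the coefficient identifies.** For one region, β = (BATA change) − (MBCT change). These three cases give the same β:
- +0.75 − 0 = 0.75
- 0 − (−0.75) = 0.75
- −0.25 − (−1.0) = 0.75

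Only the first meets the caudate criterion.

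**How often each rule is met, caudate only.** The interaction rate is the chance that t exceeds its upper critical value with noncentrality β√15. The joint rate was simulated and also requires a within-BATA t-test at two-sided 0.025 in the stated direction.

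| True change: BATA, MBCT (SD) | Interaction favours BATA | Interaction and within-BATA both met |
|---|---|---|
| 0, −0.3 | 13% | 1% |
| 0, −0.5 | 36% | 1% |
| 0, −0.75 | 73% | 1% |
| −0.25, −1.0 | 73% | 0.02% |
| +0.75, 0 | 73% | 72% |
| +0.45, −0.3 | 73% | 50% |
| +0.25, −0.5 | 73% | 17% |

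Five rows share β = 0.75, hence the same 72.6% (72.4% to 72.8% in simulations of 40,000 trials). For +0.75, 0, the same simulated trials gave 72.5% for the interaction and 72.0% for the joint rule. The last two rows are a true between-arm effect of 0.75 with both arms drifting down by 0.3 or 0.5: 0.75 − 0.3 = 0.45 and 0.75 − 0.5 = 0.25. If neither arm changes, the interaction favours BATA in half of 0.025, about 1.2%.

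**If the interaction is pooled over regions.** In the treatment by region by time model, a Treatment × Time term averaged over regions estimates the mean of the caudate and rACC differences. If BATA has the hypothesised effect, +0.75 in caudate and −0.75 in rACC with MBCT flat, the mean is (0.75 − 0.75)/2 = 0. In simulation it rejected in 2.4% of trials, which is α.

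If BATA is flat and only MBCT's caudate response falls by f, the pooled difference is f/2 with SD √((1 + ρ)/2). For an assumed between-region correlation ρ of 0.5 down to 0, it favours BATA in about 6–8%, 13–18% and 27–41% of trials for f = 0.3, 0.5 and 0.75.

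**The case against.** The strongest reply is that section 6.4 sets no declaration rule. It says the coefficient will be used in an evaluation, with the required directions written out beside it. The model contains a time term, activation is to be compared before and after treatment, and region comparisons follow. A flat BATA arm would not satisfy section 6.1. This stands in part. A reader might infer that the interaction is the only analysis planned, or that the plan would certainly declare engagement with a flat BATA arm; the documents support neither. What remains is that no within-BATA contrast is assigned to the first condition.

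Second, the randomised between-arm contrast is the causal one, and uncontrolled pre-post change mixes treatment with drift. For rACC, where the target is a fall, downward drift would even help a within-BATA test to pass. This stands as a reason to keep the interaction as a necessary condition. It does not make the interaction a measure of BATA's own change.

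Third, section 1.2 expects MBCT to act through mechanisms other than striatal reward activation, which suggests no increase rather than a decline. This also stands: the MBCT falls are illustrative. Scans at weeks 0, 8, 12 and 15 make drift possible, but nothing quantifies it.

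Finally, a reader might want to attach an inflated family-wise error rate to the post hoc region comparisons. The plan states no level for them, so no such figure can be given.

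**Conclusion.** The mismatch holds. Aim 1 has two conditions, and the coefficient assigned to both can establish only the comparative one. Under the assumed MBCT falls of 0.3 to 0.75 SD, with 30 per arm and unit SD of change, a caudate-only interaction favours a flat BATA arm in about 13% to 73% of trials, against about 1% when a within-BATA test is also required. These rates describe a per-region contrast. They are lower for a term pooled over regions when only the caudate moves, and that pooled term cannot detect the hypothesised opposite-sign effect.

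It would be tempting to add that the joint rule costs nothing. That is true only if MBCT does not change; under common downward drift the cost is large. This should be fixed before unblinded analysis. It is a gap in specification and does not invalidate the design.

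**What to change.** In section 6.4, for each region and from the same model, specify:
1. The Treatment × Time contrast at 0.025, with sidedness stated, as the comparative test. Do not pool over caudate and rACC without aligning signs.
2. The within-BATA pre-post contrast with its confidence interval, the criterion being that the interval lies on the stated side of zero (above for caudate, below for rACC).
3. The wording rule: say that BATA met the target engagement criteria only if both 1 and 2 are satisfied; if only 1 is, claim a difference from MBCT and no more.
4. Whether one region or both must satisfy the rule.

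This needs SAP wording and one further contrast per region, with no new data. The statistical cost depends on drift. It is about half a percentage point of power if BATA changes by 0.75 and MBCT does not change (72.5% to 72.0%). If both arms drift down by 0.3 or 0.5 SD, success falls from about 73% to about 50% or 17%. For that reason the comparative result should be reported in its own right, whether or not the within-BATA condition is met.

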Test Article(s) (If Applicable)	
Behavioral Activation Treatment for Anhedonia (BATA): We have modified Behavioral Activation Treatment for Depression to create Behavioral Activation Treatment for Anhedonia (BATA) which we will evaluate in this study by comparing its effects on brain functioning relative to treatment with Mindfulness-Based Cognitive Therapy (MBCT).

Study Design	Following a phone/online screen and an initial assessment session to confirm eligibility, participants will complete a baseline fMRI session at the UNC Biomedical Research Imaging Center (BRIC). They then will be randomized to receive a 15-week course of BATA (50%) or a 15-week course of Mindfulness Based Cognitive Therapy (MBCT) (50%) administered at Duke University Medical Center (DUMC). Both groups will receive pre- and post-treatment scans as well as two mid-treatment scans (weeks 8 and 12) to evaluate treatment BATA dose.
---------------------	--

Subject Population	Inclusion Criteria
key criteria for Inclusion and Exclusion:	
 1. 18-50 years old and treatment seeking; 2. SHAPS scores ≥ 20, corresponding to clinically significant anhedonia; 3. Clinician's Global Impression Scale-Severity score (CGI-S) ≥ 3 to assure a clinically impaired sample; 4. Seeking treatment for anhedonia (i.e., referred from an outpatient clinic or responded to an advertisement for anhedonia treatment; endorses desire for treatment during screening).

Exclusion Criteria

5. Those for whom medication management is the primary gold-standard treatment, including those with bipolar disorder/mania, schizophrenia spectrum, and other psychotic disorders;
6. Prior treatment with behavioral activation therapy for depression or mindfulness-based treatments (those with exposure to other forms of psychotherapy, e.g., supportive therapy, will be eligible);
7. Those who may have difficulty understanding the cognitive components of BATA, including those with intellectual disability, neurocognitive disorders, and dissociative disorders;
8. Feeding and eating disorders which may have confounding effects on the BOLD fMRI signal;
9. Substance Use Disorders given confounding effects of substances of abuse on the BOLD fMRI signal;
10. Suicidal intent and plan;

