Statistical And Analytic Plan	Aim 1: Primary Endpoint (fMRI) : Only patients who completed at least two therapy sessions will participate in post-treatment assessments. We will compare fMRI activation in regions of interest at pre- and post-treatment. The design is a 2 (BATA vs MBCT) X 2 (CN, rACC) X 2 (pretreatment vs post-treatment) ANCOVA testing the change from pre- to post-treatment as moderated by treatment group and brain region in the outcome variables. Aim 2: Secondary Endpoint : To evaluate the efficacy of BATA, relative to MBCT, for treating anhedonia, we will test for differential change over time between those who receive BATA and those who receive MBCT post-treatment. We will use an intent-to-treat (ITT) analysis for patients who receive BATA relative to those who don't. The ITT model will be a repeated-measures ANCOVA with effects for treatment condition (BATA, MBCT), outcome measure (SHAPS), time (pre-treatment, post- treatment) and their interactions. The interaction tests will assess mean differences at each time point as well as differences in the degree of change between the groups. This also provides tests of each group relative to their baseline scores. We will include gender and age as covariates in these models.
DATA AND SAFETY MONITORING PLAN	We will have an independent Data Safety Monitoring Board (DSMB) that will meet twice per year to review any adverse events as well as participant accrual and adherence/drop-outs. The members of the DSMB will be responsible for safeguarding the interests of study participants, assessing the safety of all study procedures, and monitoring the overall conduct of the study. This committee will serve as an independent advisory group to the study investigators and will provide recommendations about starting, continuing, and stopping the study.

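### Both aims test Treatment × Time on pre and post values; adjusting for the outcome's own baseline would use data already collected and is generally more precise

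*Combined protocol and SAP*

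**What the plan says.** For Aim 1, section 6.4 sets out a treatment by region by time design, labelled ANCOVA, "testing the change from pre- to post-treatment as moderated by treatment group and brain region in the outcome variables". The arm comparison rests on one term: "The Treatment × Time interaction beta will be used to evaluate whether BATA produces changes in neural responses". The Aim 1 paragraph names no covariate.

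For Aim 2, "The ITT model will be a repeated-measures ANCOVA with effects for treatment condition (BATA, MBCT), outcome measure (SHAPS), time (pre-treatment, post-treatment) and their interactions". That paragraph ends: "We will include gender and age as covariates in these models". Whether this covers Aim 1 as well, and in what form the two covariates enter, is not stated. The statistical row of the synopsis gives the same models ("We will compare fMRI activation in regions of interest at pre- and post-treatment").

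Both baselines are collected: the scan at week 0 (section 5) and SHAPS before treatment (section 4.2). Randomisation is stratified on SHAPS, 20–30 against 31 and above (sections 3.2 and 8). The stratum appears in neither model.

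**The concern.** The word ANCOVA suggests baseline adjustment, but the pre-treatment value is a response in these models, so they contain none. Gender and age do not stand in for it. For one outcome measured twice with complete data, the Treatment × Time test is the two-sample comparison of change scores. It is unbiased under randomisation, it answers the stated question, and it does not inflate type I error.

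What is at stake is precision. The trial has 60 patients, 30 per arm, and the comparison with MBCT is part of the primary aim. In large samples, conditioning on the outcome's own baseline is never less precise than subtracting it, and it is often more precise.

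For SHAPS there is a second effect. Stratified allocation already balances part of the baseline, but a model that omits both stratum and baseline takes no credit for this in its standard error. The test can then be conservative.

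The adjustment needs a baseline taken before randomisation. The synopsis says "participants will complete a baseline fMRI session at the UNC Biomedical Research Imaging Center (BRIC). They then will be randomized", and section 4.8 agrees: if the delay is too long before "the first scan session, this will be considered a screen fail and the individual will not be randomized". Section 4.1, however, lists randomisation above the pre-treatment scan, and the section 4.2 schedule puts both on Day 1.

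**Working it through.** **Inputs from the documents.** 60 randomised 1:1, so 30 per arm (synopsis); alpha 0.025, power above 90% and an effect range of 0.75–1.25 labelled z (section 6.5). Sidedness, ρ, k and a dropout rate are not given.

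**The plan's own figure.** I read 0.75–1.25 as a between-arm difference in change-score SDs for one region. Section 6.5 does not say this. Noncentral t, 30 per arm, 58 df, two-sided 0.025:

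- 0.75: 73% (82% if 0.025 is one-sided)
- 1.0: 94%
- 1.25: 99%

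On this reading the claim of more than 90% holds in the middle and at the top of the range but not at 0.75. The precision argument does not depend on it.

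**Variance.** In units of the post-treatment variance:

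- change score: 1 + k² − 2ρk
- baseline-adjusted: 1 − ρ²
- difference: (k − ρ)², which is never negative and is zero at ρ = k

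Example, k=1 and ρ=0.5: 0.75/1.00 = 0.75. Example, k=0.7 and ρ=0.3: 0.91/1.07 = 0.85.

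**Grid (ρ and k assumed).** The per-arm equivalent is the size a change-score analysis needs to match an adjusted one with 30 per arm, 30/ratio. Power is at 0.75 change-score SDs, with ratio × (1+1/56) for estimating the slope and 57 df; the unadjusted figure is 73%.

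| k | ρ | Ratio | Per-arm equivalent | Adjusted power |
|---|---|---|---|---|
| 1 | 0.3 | 0.65 | 46 | 89% |
| 1 | 0.5 | 0.75 | 40 | 84% |
| 1 | 0.7 | 0.85 | 35 | 79% |
| 0.8 | 0.3 | 0.78 | 38 | 83% |
| 0.8 | 0.5 | 0.89 | 34 | 77% |
| 0.8 | 0.7 | 0.98 | 31 | 73% |
| 0.7 | 0.3 | 0.85 | 35 | 79% |
| 0.7 | 0.5 | 0.95 | 32 | 74% |
| 0.7 | 0.7 | 1.00 | 30 | 72% |

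Leaving out the slope cost raises each power by less than one point. At 1.0, 94% becomes 97–99% (k=1) or 94–97% (k=0.7). At 1.25 power is about 99% or more either way.

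**If 0.75 is instead in post-treatment SD units** (slope cost omitted), for ρ = 0.3, 0.5, 0.7:

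- k=1: 56, 73, 92% unadjusted; 77, 85, 96% adjusted
- k=0.7: 69, 83, 96% unadjusted; 77, 85, 96% adjusted

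**SHAPS under stratified allocation.** This was simulated with all inputs assumed: N=60, blocks of 4 within the two strata, integer baseline from a normal with mean 30 or 34 and SD 6 truncated at 20, one SHAPS value serving as entry score, stratifier and baseline, 20,000 runs per setting. Ranges are over the two means and the three ρ values.

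| | k=1 | k=0.7 |
|---|---|---|
| True variance, adjusted/change score | 0.80–0.94 | 0.93–1.01 |
| Change-score SE²/true variance | 1.09–1.29 | 0.99–1.10 |

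A further 6,000-run check at mean 30 and k=1 gave change-score type I error of 0.010, 0.014 and 0.020 (ρ = 0.3, 0.5, 0.7) against a nominal 0.025. The adjusted test gave 0.025–0.027. Adding the stratum on top of continuous baseline SHAPS raised the estimated variance by 1.0–1.3%.

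**The case against.** The planned test is valid and estimates the differential change the plan asks about, so this is a choice between two sound estimators. The gain is unknown: on the grid above it runs from about a third of the variance to nothing, and at effects of 1.0 or more power is already high. For SHAPS the low-k rows may be the more realistic ones. Entry at 20 or above truncates baseline but not post-treatment scores, and stratification has already used part of the baseline information. Adjustment also has a cost: at ρ = k = 0.7, power at 0.75 falls from 72.6% to 71.7%, and to 70.8% if an uninformative stratum is added as well. Finally, estimating each region separately changes the shape of Aim 1, and a post-treatment ANCOVA does not give within-arm change.

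Most of this stands as a limit on size. No single gain can be promised, and none is expected near ρ = k. It does not reverse the recommendation: the worst loss shown is under two points of power, against a possible gain of about 16 points (73% to 89%). Section 6.1 already states the endpoint region by region, with opposite expected directions, and an alpha of 0.025 is compatible with two region-level tests. Within-arm changes can be reported alongside an ANCOVA or taken from a longitudinal model.

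**Conclusion.** The point holds as an improvement in efficiency. The planned analysis contains no bias and no inflated type I error. Neither aim adjusts for a baseline that the trial already collects, and the SHAPS stratum is in neither model. On assumed ρ of 0.3–0.7 and k of 0.7–1, the large-sample reduction in variance is between 35% and nil. It matters mainly at the low end of the planned effect range. For SHAPS the true gain is smaller, because allocation is stratified on it (6–20% at k=1, 7% to nil at k=0.7), but adjustment also removes the conservatism of the unadjusted test where that occurs. Confidence in the size is moderate, because ρ, k and the scale of the planning effect are all assumptions. The recommendation itself rests only on randomisation and on a baseline taken before it.

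**What to change.** - For each region in Aim 1, and for SHAPS in Aim 2, estimate the post-treatment arm difference adjusted for that outcome's own pre-randomisation baseline. Adding baseline as a covariate to a model in which it is already a response is not the way to do this.
- Name one form in advance: ANCOVA on the post-treatment value, or a longitudinal model with a common baseline mean across arms. They can differ when post-treatment data are missing, because patients with only a baseline enter the second and not the first. Sections 4.7 (dropout) and 6.4 ("Only patients who complete at least two therapy sessions will participate in post-treatment assessments") make such patients foreseeable. They can also differ when the regions are modelled jointly, since a joint model conditions on both baselines. With equal SDs and ρ=0.5, residual variance given both was 0.83–1.00 of that given one, over assumed region correlations of 0.2–0.6 and cross-region pre-post correlations of 0–0.45.
- Keep the region comparison and the within-arm change estimates as planned.
- Include the SHAPS stratum in the Aim 1 model so that the analysis reflects the randomisation. In Aim 2, continuous baseline SHAPS already covers it.
- State which aims gender and age apply to.
- Confirm that the baseline scan precedes randomisation, reconciling sections 4.1 and 4.2 with the synopsis and section 4.8. State which SHAPS reading is the baseline, since it is taken at screening and again before treatment.

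The cost is SAP wording and a few degrees of freedom: one for the baseline, and one for the stratum in Aim 1. No new data are needed.
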